7.2 +/-ml reduction in mean lumbosacral CSF volume lasting for 30+ minutes and alterations in CSF velocity waveform, both associated with a 5 to 15 ml epidural volume injection with an intact dura.³ Our study is designed to better understand the clinical effects and mechanism of pre-existing epidural injectate volume effect on subsequently performed spinal block.

Objective:

To compare in a controlled, randomized prospective fashion the clinical effect and mechanism of pre-existing epidural saline volume effect on subsequently performed spinal block. Our hypothesis is that 15 ml of a pre-existing epidural injectate volume will significantly increase the level of sensory block and increase the analgesic duration of action in a subsequently performed spinal block.

Methods and Measures

Design and Outcome Measures: This study is a prospective randomized double-blind study whereby the patients will be randomized to one of two groups with either 0 ml or 15 ml of epidural saline injections followed by injection of 3 mg of isobaric bupivacaine intrathecally. Primary outcome measures are highest sensory blockade level to pinprick and to cold. We divided anesthesia dermatome levels to a total of 20 levels from sacral (1 level) then L5 to T1 (as 17 levels) and then C7 (1 level) and C6 or higher as another level. Modified Bromage Motor Scale will be used to assess the amount of motor blockade in the lower extremities.

Secondary outcome measures are the following:

- 1.) Time to Onset of analgesia (VAS <=3)
- 2.) Duration of analgesia (time to request additional analgesia)
- 3.) Time to highest sensory blockade level
- 4.) Time for 2 dermatome level regression of sensory block
- 5.) Time for regression of motor blockade
- 6.) Occurrence of common spinal/epidural side effects: hypotension, fetal bradycardia, vasopressor use (ephedrine), excessively high blocks (higher than T4) and postdural puncture headache

Setting: The study will take place on the labor and delivery suite at Forsyth Medical Center.

Protocol and Procedures:

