A. 90 healthy women with uncomplicated pregnancies in early labor (≥ 2 cm but ≤ 6 cm cervical dilation) requesting neuraxial analgesia will be consented to participate to obtain 60 evaluable subjects enrolled in this randomized controlled trial. Patients will be greater than 12 years of age, have an assigned ASA physical status 1 or 2 with a singleton pregnancy. Patients with contraindications to neuraxial anesthesia, inappropriate for study, or with allergies to drugs used in the study will be excluded. Patients inappropriate for study would include those with an assigned ASA status 3 or 4, advanced labor (> 6 cm cervical dilation) or less than 12 years of age. Patients with the potential for distorted epidural anatomy, such as Harrington rods or prior back surgery, will also be excluded.

B. Patients will be randomized into 1 of 2 groups:

Group 1. 45 subjects Epidural space will be identified with loss of resistance to minimal air or saline ($<0.2-0.3$ ml) with a 17 gauge epidural needle. Then, after 20-30 seconds, the spinal needle will be inserted via the epidural needle in the usual manner and 3 mg isobaric bupivacaine (1.2 ml of 0.25% isobaric bupivacaine) will be given intrathecally.

Group 2. 45 subjects Epidural space will be identified with loss of resistance to minimal air or saline ($<0.2-0.3$ ml) with a 17 gauge epidural needle. Normal saline 15 ml will then be administered through the epidural needle over approximately 20 seconds and held for another 10 seconds. The spinal needle will then be inserted via the epidural needle in the usual manner and 3 mg isobaric bupivacaine (1.2 ml of 0.25% isobaric bupivacaine) will be given intrathecally.

In both groups after administration of intrathecal study drug, the spinal needle will be removed followed by insertion of the epidural catheter as in the usual manner. After placement of the epidural catheter, patients will be returned to the supine position with slight left tilt. Patients will be placed with their head up at an angle of approximately fifteen degrees after the spinal injection. The epidural catheter will not be tested or dosed until the patient requests further analgesia. When additional analgesia is requested, the epidural catheter will be tested and dosed in the customary fashion. The catheter will then be connected to a patient controlled epidural analgesic pump with the settings as per our normal standard of care.

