C. All patients will be required to sign an informed consent document prior to participating in the study.

We anticipate that it will take 24 months to enroll and study 60 evaluable patients. The specifics of the research will be explained to patients and any questions will be answered. Patient confidentiality will be maintained.

D. All patients will have a functioning intravenous catheter and receive appropriate intravenous fluid of balanced salt solution prior to insertion of their epidural catheter. The epidural space will be located by the usual technique with the patient in the sitting position using a 17G epidural Tuohy sited at L₃₋₄ +/- 1 intervertebral space. All patients will then have an 18G epidural catheter inserted the customary length (5 cm) into the epidural space. The epidural needle will be removed and the catheter secured.

E. Background information on age, height, weight, gestation age, gravid status, cervical dilation, pitocin usage, and stadol usage will be obtained from patient report or the medical record. Study participants will indicate their level of discomfort at peak contraction on a standard 0-10 verbal analog scale (VAS). We will monitor and record the dermatome, pain score, vital signs, ephedrine usage, maternal vital signs, and fetal heart rate every 5 minutes for 20 minutes after initial spinal drug administration or every 5 minutes for 15 minutes after each subsequent physician epidural drug administration. Patient will also be assessed every 15 minutes until the patient requests additional analgesia. Changes in sensory levels to temperature and pin prick perception will also be assessed using alcohol pads and dull pins, respectively, at these same time intervals. Patients will be monitored in the usual clinical manner. Side effects such as hypotension, fetal bradycardia and post dural puncture headache will be recorded and treated as in our usual clinical practice. Participants will have their need for additional medication be evaluated in the routine fashion, and the amount and type of drug administered will be recorded.

Statistical and Analytical Plan:

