SigmaStat for Windows by SPSS Inc is being used for statistical analysis. Based on previous observations and our obstetric anesthesia unit quality assurance data, we estimated one standard deviation of our primary outcome measure (highest sensory dermatome level of block) to be 3 dermatome levels. We considered a clinically significant difference in highest sensory block dermatome level between groups to be 3 dermatome levels. With these assumptions and to detect at least a 3 dermatome level difference in highest sensory block between groups with a power of 0.8 to 0.9 and an alpha of 0.05, the minimum sample size

needed is 30 patients per group. For the secondary outcome measure (analgesic duration of action), we consider a difference of 15 minutes between groups to be clinically significant with an estimated 60 minutes for mean duration of action and a standard deviation of 15 minutes. Similarly, the minimal sample size required to detect a difference of 15 minutes or more in analgesic duration between groups is 23 per group with a power of 0.8 to 0.9 and alpha of 0.05. Furthermore, based on our clinical quality assurance report, labor CSE and epidural analgesia may have up to 30% needing additional supplemental dosing and/or technical technique adjustments to achieve complete labor analgesia. Therefore, we will plan to enroll 45 patients per group to obtain at least 30 evaluable patients per group. The primary outcome in dermatome level difference will be analyzed by ANOVA on ranks using Kruskel Wallis test followed by posthoc Tukey test as appropriate.

Risks:

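### 'Evaluable' is undefined and no analysis set is named, while the 45-to-30 sizing implies, without saying so, that randomised patients are dropped for an event that may depend on block adequacy

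*Combined protocol and SAP*

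**What the plan says.** Three places size the trial on evaluable patients.

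- Protocol and Procedures, paragraph A: 90 women "will be consented to participate to obtain 60 evaluable subjects enrolled in this randomized controlled trial". Paragraph B then lists 45 subjects in each of the two randomised groups.
- Paragraph C: "We anticipate that it will take 24 months to enroll and study 60 evaluable patients".
- Statistical and Analytical Plan: the unit's quality assurance data suggest that labor CSE and epidural analgesia "may have up to 30% needing additional supplemental dosing and/or technical technique adjustments to achieve complete labor analgesia". The next sentence draws the conclusion: "Therefore, we will plan to enroll 45 patients per group to obtain at least 30 evaluable patients per group".

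No section defines the term, names an as-randomised or any other analysis set, or says how failed or supplemented blocks are handled. The plan for the primary outcome names only the rank test.

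Three other statements bear on the point. Paragraph B says: "The epidural catheter will not be tested or dosed until the patient requests further analgesia". Paragraph E schedules assessments every 5 minutes for 20 minutes and adds: "Patient will also be assessed every 15 minutes until the patient requests additional analgesia". Design and Outcome Measures defines the primary scale: "We divided anesthesia dermatome levels to a total of 20 levels from sacral (1 level) then L5 to T1 (as 17 levels"), followed by C7 and by C6 or higher. The scale has no category for an absent block. Time to the request for more analgesia is itself a secondary outcome.

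**The concern.** The only event offered to explain the loss from 45 to 30 is incomplete analgesia that needs more drug or a change of technique. It occurs after allocation, and the Objective predicts that saline raises the block and lengthens analgesia, so its frequency may differ by arm. If those patients are dropped, the comparison is no longer the randomised one. Dropping patients who need early supplementation would also remove short values of the duration outcome.

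Most such exclusions would be unnecessary. The catheter is not used until the request, so spinal-phase levels and the time of the request are normally on record before any supplementation or catheter failure. A failed or repeated placement may leave no such data. With no written rule, evaluability could also be decided after outcomes are known, and the documents do not say who decides it.

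**Working it through.** **1. The plan's own figure.** Inputs from the Statistical and Analytical Plan: 30 per group and up to 30% affected. 30/(1 − 0.30) = 42.9, so 43; the plan's 45 is two more. 45 to 30 allows a loss of 15/45 = 33.3%; at 30% loss, 45 × 0.70 = 31.5 remain. The 45 therefore fits a reading in which the affected patients do not count as evaluable. The Risks section gives 20–32% for an epidural that does not function properly; 30/0.68 = 44.1, so 45. A catheter-failure allowance fits at least as well.

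**2. Where the loss falls.** The 45 per randomised group in paragraph B, and enrolment counted per group, point to loss after allocation. The word 'consented' in paragraph A leaves room for some loss before it.

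**3. What exclusion could do.** The plan gives SD 3 and difference 3. The rest is assumed: 30% of controls dropped, and a latent adequacy score with correlation ρ to block level. If all loss is block-related, with c = Φ⁻¹(0.30) = −0.524 and λ(a) = φ(a)/(1 − Φ(a)):

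observed difference = 3 + 3ρ[λ(c − ρ) − λ(c)]

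For ρ = 0.7: 3 + 2.1 × (0.212 − 0.497) = 2.40. If only a share of the 30% is block-related, c is set to that share and the rest is dropped at random.

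| Share of loss that is block-related | ρ = 0 | 0.5 | 0.7 | 1.0 (extreme) |
|---|---|---|---|---|
| a quarter | 3.0 | 2.9 | 2.8 | 2.6 |
| half | 3.0 | 2.8 | 2.6 | 2.3 |
| all | 3.0 | 2.7 | 2.4 | 1.9 |

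Simulated rank-test power, starting from 45 per group, is 0.97 / 0.96 / 0.95 / 0.93 for half and 0.97 / 0.96 / 0.95 / 0.90 for all. The plan's target of 0.8 to 0.9 is met throughout. For duration (difference 15 minutes, SD 15, the same standardised effect), multiply levels by 5: half gives 15.0 / 13.9 / 13.1 / 11.6 minutes.

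**4. Direction.** Suppose 70% of controls are kept and a proportion r of saline patients, with all loss block-related:

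bias = 3ρ[φ(z_r)/r − φ(z_0.70)/0.70], where z_p = Φ⁻¹(p)

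At ρ = 0.7 and r = 0.60: 2.1 × (0.644 − 0.497) = +0.31 levels. For r = 0.80 / 0.60 / 0.50 the bias is −0.31 / +0.31 / +0.63, and the simulated type I error with no effect on level is 0.08 / 0.07 / 0.14. With equal loss it stays near 0.05.

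**5. What keeping the patients gives.** Simulated rank-test power at a difference of 3 is about 0.996 with 45 per group and 0.96 with 30. If 5 / 10 / 15 / 20% of both arms are placed at the lowest rank, power with 45 per group is about 0.98 / 0.95 / 0.88 / 0.79.

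**The case against.** The strongest reply is that no exclusion is written anywhere. The 30% is a unit-wide figure for CSE and epidural analgesia together, and it mixes supplementation with technical adjustments. With the 20–32% malfunction rate under Risks, a catheter-related allowance is plausible; it could be almost unrelated to spinal level, and then there is no bias. All of this stands, and it limits the point to an undefined term and an implied practice.

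The reply also holds that the 20-level scale merely codes blocks that exist, and does not say that a patient without one is excluded. That is fair: a lowest category clarifies the coding. It is still needed, because such a patient has no defined score.

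A further objection is that ranking patients who never received a spinal at the bottom of the primary analysis answers a different question from the Objective, which concerns a spinal block that was performed. It is also costly. With such failures in 10% of controls and 20% of saline patients, power at a difference of 3 is about 0.6, and with no effect on level the test rejects in about 13% of trials. This stands too, and such patients belong in a sensitivity analysis.

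A reader might infer that the plan commits to a biased per-protocol analysis, that the bias favours saline, or that the trial would be underpowered. The documents support none of these. Exclusion is only implied, loss by arm and its link to level are not given, and power stays at 0.90 or above in the attenuation cases of step 3.

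**Conclusion.** The point holds as a gap in the analysis plan that should be fixed, with medium confidence. The missing definition and analysis set are plain from the text. That randomised patients would be dropped is an inference from the sizing, and that the loss depends on block adequacy is a possibility.

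No size or direction of bias can be taken from the documents. The range from 3.0 down to 1.9 levels, the shifts of −0.3 to +0.6 and the type I error of up to 0.14 all rest on assumed correlations, loss shares and retention rates. The type I figures further require all loss to be block-related and to differ by arm although saline leaves level unchanged. The case rests on the validity of the comparison and on discarding up to 30% of patients, many of whom would have usable spinal-phase data.

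**What to change.** State the following before unblinding:

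- **Primary set:** all randomised patients who received the intrathecal injection, analysed by assigned group, using the highest level recorded from that injection to the first epidural drug dose.
- **No exclusions** for supplementation, early request or later catheter failure.
- **Absent block** after a given spinal: coded as the lowest rank, below sacral.
- **Duration:** any request for additional analgesia, however early, counts as the event.
- **No intrathecal drug given:** report by arm with reasons. In Group 2 the saline comes first ("Normal saline 15 ml will then be administered through the epidural needle over approximately 20 seconds and held for another 10 seconds"), so this loss could itself differ by arm. Include these patients at the lowest rank in a sensitivity analysis only.
- **Evaluable-only analysis:** if kept, a sensitivity analysis, with the term defined in writing and exclusions reported by arm.

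The cost is a little more analysis work and some dilution if blocks fail for reasons unrelated to treatment: at the planned difference, power stays near 0.95 with 10% absent blocks in both arms and falls to about 0.79 with 20%. No extra patients or visits are needed, since 45 per group and assessments up to the request are already planned.
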